**8.1 Dose Levels (Based on Adverse Events in Tables 8.2 and 8.3)**

Dose Level	Ixazomib	Ibrutinib
Starting Dose	4.0 mg	420 mg
-1	3.0 mg	280 mg
-2	2.3 mg	140 mg
-3	Discontinue	Current dose

NOTE: If ixazomib is discontinued, the patient can continue on single-agent ibrutinib at the dose the patient is on when ixazomib is discontinued.

→ → Use the NCI Common Terminology Criteria for Adverse Events (CTCAE) current version 4.0\* unless otherwise specified ← ←

\* Located at [http://ctep.cancer.gov/protocolDevelopment/electronic\\_applications.ctc.htm](http://ctep.cancer.gov/protocolDevelopment/electronic_applications.ctc.htm)

## 8.2 Ixazomib dose modifications

CTCAE System/Organ/Class (SOC)	ADVERSE EVENT	AGENT	ACTION**
Investigations	Neutrophil count decreased Grade 4		*Omit dose until AE has resolved to Grade 2 or better • Follow CBC weekly * If neutropenia has resolved to $\leq$ Grade 2, resume dose at one level lower *If, after ixazomib has been omitted, and the AE does not return to $\leq$ Grade 2 within 4 weeks, then the patient may continue on single-agent ibrutinib till the completion of treatment and then proceed to survival follow-up
Blood and lymphatic system disorders	Febrile neutropenia $\geq$ Grade 3	Ixazomib	• Omit dose and follow CBC weekly • If neutropenia has resolved to $\leq$ Grade 2, resume dose at same level with GCSF support (See Section 9.2)
Investigations	Platelet count decreased Grade 4		*Omit dose until AE has resolved to Grade 1 or better • Follow CBC weekly • If thrombocytopenia $<25,000/\text{mm}^3$ recurs, reduce dose by one dose level and continue therapy when platelet count $\geq 75,000/\text{mm}^3$ If, after ixazomib has been omitted, and the AE does not return to $\leq$ Grade 1 within 4 weeks, then the patient may continue on single-agent ibrutinib till the completion of treatment and then proceed to survival follow-up

CTCAE System/Organ/Class (SOC)	ADVERSE EVENT	AGENT	ACTION**
Nervous System Disorders	Peripheral Motor Neuropathy and Peripheral Sensory Neuropathy. Grade 2 or Grade 1 with pain		Omit ixazomib until resolution to Grade $\leq$ 1 without pain or baseline. *If, after ixazomib has been omitted, and the AE does not return to $\leq$ Grade 1 within 4 weeks, then the patient may continue on single-agent ibrutinib till the completion of treatment and then proceed to survival follow-up
	New or worsening Grade 2 peripheral motor neuropathy and peripheral sensory neuropathy with pain or Grade 3		Omit ixazomib until resolution to Grade $\leq$ 1 without pain or baseline and then reduce ixazomib to next lower dose upon recovery. *If, after ixazomib has been omitted, and the AE does not return to $\leq$ Grade 1 within 4 weeks, then the patient may continue on single-agent ibrutinib till the completion of treatment and then proceed to survival follow-up.
	New or worsening Grade 4 peripheral neuropathy		Discontinue ixazomib. The patient may continue on single-agent ibrutinib till the completion of treatment and then proceed to survival follow-up.

\*\* Use the following to describe actions in the Action column:

- **Omit** = The current dose(s) for the specified drug(s) during a cycle is skipped. The patient does not make up the omitted dose(s) at a later time.
- **Hold/Delay** = The current dose(s) of all drugs during a cycle is delayed. The patient does make up the delayed dose(s) when the patient meets the protocol criteria to restart drugs.
- **Discontinue** = The specified drug(s) are totally stopped.

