#### Additional Adverse Events:

Grade  $\geq 3$  non-hematological toxicity (other than peripheral neuropathy) considered at least probably related to ixazomib:

- Omit ixazomib until resolution to Grade  $\leq$  1 or baseline, then restart at the same dose.
- If not recovered to  $\leq$  Grade 1 or baseline despite adequate supportive care within 4 weeks, then the patient may continue on single-agent ibrutinib till the completion of treatment and then proceed to survival follow-up.
- For reoccurrence of  $\geq 3$  non-hematological toxicity (other than peripheral neuropathy) omit ixazomib until resolution to Grade  $\leq$  1 or baseline, then restart at one lower dose level.
- **For  $\geq 3$  nausea, vomiting or diarrhea:** Once the ixazomib is omitted and the toxicity recovers to Grade  $\leq$  1 or baseline within 4 weeks of holding ixazomib, it should be restarted at one lower dose level.
- Once ixazomib is reduced for any toxicity, the dose may not be re-escalated. If it is ultimately determined that therapy with ixazomib is no longer safe, the patient may continue on ibrutinib until completion of treatment and then proceed to survival follow.

- If multiple AEs are seen, administer the dose based on the greatest reduction required by any single AE observed. Dose modifications are for AEs attributed to study treatment only. Dose modifications are not required for AEs if they are deemed unlikely or unrelated to study treatment.

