## 8.3 Ibrutinib dose modifications

CTCAE System/Organ/Class (SOC)	ADVERSE EVENT	AGENT	ACTION**
Investigations	Neutrophil count decreased Grade 4	Ibrutinib	If the AE does not return to $\leq$ Grade 2 after reduction of ixazomib to 2.3 mg, then reduce ibrutinib dose as per table 8.1. If no recovery on the 140 mg dose level, then discontinue study therapy and then proceed to survival follow-up.
Investigations	Platelet count decreased Grade 4		If the AE does not return to $\leq$ Grade 1 after reduction of ixazomib to 2.3 mg, then reduce ibrutinib dose as per table 8.1. If no recovery on the 140 mg dose level, then discontinue study therapy and then proceed to survival follow-up.

\*\* Use the following to describe actions in the Action column:

- **Omit** = The current dose(s) for the specified drug(s) during a cycle is skipped. The patient does not make up the omitted dose(s) at a later time.
- **Hold/Delay** = The current dose(s) of all drugs during a cycle is delayed. The patient does make up the delayed dose(s) when the patient meets the protocol criteria to restart drugs.
- **Discontinue** = The specified drug(s) are totally stopped.

Additional Adverse Events:

- The dose of ibrutinib will be omitted in case a patient experiences any of the following considered at least possibly related to ibrutinib:
  - Any Grade  $\geq 3$  or greater non-hematological toxicities (other than alopecia or fatigue) with the following considerations:
    - Grade 3 nausea, vomiting or diarrhea will be considered significant if they occur despite appropriate maximal anti-emetic and/or antidiarrheal therapy.
    - Grade 3 hyperglycemia will be a considered significant if the patient is symptomatic or glucose level is  $>300$  mg/ml despite appropriate administration of insulin and/or oral antidiabetic agents.
- Ibrutinib will be omitted until the non-hematologic AE recovers to Grade  $\leq 1$  or baseline and may be restarted at the original dose for the first occurrence.
- Upon each subsequent occurrence, ibrutinib is restarted at the next lower dose (as per Table 8.1) after recovery to Grade  $\leq 1$  or baseline.

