## 13.0 Treatment/Follow-up Decision at Evaluation of Patient

Reason Off Treatment (from the Off Treatment Form)	Go to CFU, SFU, or end folder rollout
1 = Treatment (Intervention) Completed Per Protocol Criteria	CFU

2 = Patient Withdrawal/Refusal After Beginning Protocol Therapy (Intervention)	SFU
3 = Adverse Events/Side Effects/Complications	SFU
4 = Disease Progression, Relapse During Active Treatment (Intervention)	SFU
5 = Alternative Therapy	SFU
6 = Patient Off-Treatment (Intervention) For Other Complicating Disease	SFU
7 = Death On Study	No follow-up
8 = Other	SFU
10 = Disease Progression Before Active Treatment (Intervention)	No follow-up
24 = Patient Withdrawal/Refusal Prior To Beginning Protocol Therapy (Intervention)	No follow-up

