### 13.3 Off protocol treatment

Patients who go off protocol treatment for the following reasons will go to the survival follow-up phase per Section 4.2:

- Progressive Waldenstrom's macroglobulinemia at any time on the clinical trial
- Patient requests to discontinue study treatment
- Patient develops an intercurrent illness that precludes further participation, or requires a prohibited concomitant treatment
- The Investigator withdraws the patient in the patient's best interests
- Administrative reasons (e.g., the patient is transferred to hospice care)
- An adverse event, which in the opinion of the Investigator, precludes further trial participation
- A dose omission of more than 28 days beyond the scheduled date of retreatment for ixazomib and ibrutinib

All attempts should be made to complete the End of Treatment procedures if a patient goes off treatment early.

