### 13.4 Clinical follow-up

If the patient has achieved CR, VGPR, PR, MR, or SD after the completion of 24 cycles of study treatment, the patient will be observed every 3 months for 2 years. After the completion of clinical follow-up, the patient will go to survival follow-up per Section 4.2 of the protocol. If the patient has progressive disease or receives subsequent treatment for Waldenstrom macroglobulinemia at any time while in clinical follow-up, the patient will go directly to survival follow-up.

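### Section 8.2 sends patients who finish on ibrutinib alone to survival follow-up, but 13.0 and 13.4 send non-progressing 24-cycle completers to clinical follow-up

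*Combined protocol and SAP*

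**What the plan says.** **Treatment after ixazomib is stopped.** Section 8.1 allows treatment to go on with one drug: "If ixazomib is discontinued, the patient can continue on single-agent ibrutinib at the dose the patient is on when ixazomib is discontinued". Section 8.2 then states where these patients go. The recurring instruction in its table is "then the patient may continue on single-agent ibrutinib till the completion of treatment and then proceed to survival follow-up". The last bullet of the additional adverse events text in 8.2 says the same in slightly different words: "the patient may continue on ibrutinib until completion of treatment and then proceed to survival follow".

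**Follow-up after completion.** Section 13.0 lists reasons for going off treatment beside a column headed "Go to CFU, SFU, or end folder rollout". The reason "1 = Treatment (Intervention) Completed Per Protocol Criteria" is routed to CFU, clinical follow-up. Section 13.4 begins "If the patient has achieved CR, VGPR, PR, MR, or SD after the completion of 24 cycles of study treatment" and prescribes observation every 3 months for 2 years. Survival follow-up comes after that, or earlier if the patient progresses or starts new treatment. Neither section makes an exception for patients who finished on ibrutinib alone. The overview in Section 1.4 gives the same order, though it is not an independent rule.

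**Content of the two phases.** The clinical follow-up column of the Section 4.1 test schedule includes examination, blood count, immunoglobulins, SPEP, immunofixation, free light chains and tumor measurement. The survival follow-up table in Section 4.2 has one row, event monitoring, every 3 months until progression or subsequent treatment.

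**The concern.** A patient who drops ixazomib for toxicity, stays on ibrutinib and reaches the end of cycle 24 without progression satisfies both 8.2 and 13.4, and the two give different instructions. Nothing in the protocol says which prevails.

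The choice matters for TTP, which Section 16.322 measures from registration to the earliest documented progression. Under Appendix III, progression by IgM needs a measured rise of at least 25% from nadir, confirmed by a second measurement 4 weeks apart, and a rise of at least 500 mg/dL if IgM is the only evidence. Without scheduled measurements, biochemical progression may be documented later or missed. The affected patients are selected by toxicity, so TTP would be ascertained unevenly across the trial population.

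Patients who stop all treatment early go to survival follow-up by design and are not part of this point.

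**Working it through.** The plan gives no figure here to reproduce. The check compares the routing texts and then counts the scheduled assessments at stake.

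**1. Instructions in 8.2.** The table has five: neutrophils, platelets and three neuropathy rows. The additional adverse events bullets have two: non-hematological toxicity not recovered within 4 weeks, and ixazomib judged no longer safe. 5 + 2 = 7.

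**2. The same patient under each section.** Take a patient whose ixazomib is stopped for toxicity, who completes 24 cycles on ibrutinib and has stable disease or better.

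| Section | Does it apply? | Route |
|---|---|---|
| 8.2 | Yes: finished on ibrutinib alone | Survival follow-up |
| 13.0, code 1 | Yes: treatment completed | Clinical follow-up |
| 13.4 | Yes: stable disease or better after 24 cycles | Clinical follow-up, then survival follow-up |
| 13.3, adverse-event item | No: it requires "An adverse event, which in the opinion of the Investigator, precludes further trial participation", and this patient completed treatment | Not applicable |
| 8.3, persistent cytopenia | No: the instruction is "then discontinue study therapy and then proceed to survival follow-up", and this patient did not stop study therapy | Not applicable |

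Section 8.3 also covers the mirror case. A patient who stops ibrutinib at the lowest dose, or after 4 weeks of omission, may continue ixazomib alone, and that text adds no survival follow-up instruction. A 24-cycle completer in that group falls under 13.4. The two single-agent groups are thus treated differently, with no reason given.

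**3. Scheduled rows.** Section 4.1 marks these for clinical follow-up: examination, blood count, chemistry, bone marrow, SPEP/UPEP, immunoglobulins, immunofixation, free light chains, beta-2-microglobulin/LDH/viscosity, tumor measurement, EKG/ECHO/MUGA and adverse event monitoring. That is 12 rows, of which bone marrow and EKG/ECHO/MUGA are only as clinically indicated. Section 4.2 marks 1.

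**4. Timing** (30.4375 days per month).
- End of treatment: 24 × 28 = 672 days; 672 / 30.4375 = 22.1 months.
- End-of-treatment visit: 672 + 28 = 700 days; 700 / 30.4375 = 23.0 months.
- End of clinical follow-up: 22.1 + 24 = 46.1 months, or 23.0 + 24 = 47.0 months from treatment start.

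**5. Assessments lost per affected patient if 8.2 is followed.**
- No progression in the 2 years: 24 / 3 = 8.
- Progression 12 months into the period: 12 / 3 = 4.
- Progression 6 months into the period: 6 / 3 = 2.

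Under 13.4 these assessments are scheduled. Under 8.2 none are scheduled after the end-of-treatment visit.

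**The case against.** The strongest counter-reading is that 8.2 is a deliberate specific rule that overrides the general one. Seven consistent statements do not look like a single slip. However, no section says that 8.2 takes precedence, no rationale is given, and the mirror case in 8.3 points the other way.

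A second reading is that survival follow-up in 8.2 is only the eventual destination, since every completer reaches it after clinical follow-up. Section 8.2 does not say *directly*, a word that 13.4 uses when clinical follow-up is cut short. But 13.2 and 13.3 also omit the word, and 8.2 goes from completion of treatment to survival follow-up without mentioning clinical follow-up. If this is the intent, the proposed edit makes it explicit.

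Other texts might seem to support 8.2:
- The last item in 13.3 sends patients to survival follow-up after a dose omission of more than 28 days, close to the 4-week trigger in 8.2. It names both drugs and covers only patients who go off protocol treatment.
- The bleeding rule in 8.3 names ibrutinib alone, but it sends the patient to survival follow-up at discontinuation, not after completing treatment.
- Section 18.5 asks for supporting documents on progression after study therapy. It collects tests that were done and schedules none.

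Some limits stand. The row count of 12 against 1 does not measure endpoint loss: chemistry and adverse event rows are included, UPEP after baseline is discretionary and no scan is mandatory. TTP is a descriptive Kaplan-Meier endpoint with no test. Patients who stop early already go to survival follow-up, so some unevenness exists regardless. Event monitoring keeps the same 3-month interval, so what is at risk is the protocol schedule of tests, not all knowledge of progression.

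**Conclusion.** The contradiction is in the current text and holds. Its consequence is conditional and minor. Where the 13.0 code selects the follow-up folder, nothing is lost. Where 8.2 is followed, the ceiling is 8 scheduled disease assessments per affected patient, at about months 22 to 46 from treatment start (23 to 47 if counted from the end-of-treatment visit), and fewer if progression comes earlier.

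This assumes that *completion of treatment* in 8.2 includes reaching 24 cycles without progression, and that no site instruction outside the protocol settles the route. The number of affected patients cannot be derived from the documents, so no overall effect on the TTP estimate can be given. The complete response decision rule is essentially unaffected: Section 16.6 ties primary endpoint completion to the end of 24 cycles or earlier discontinuation.

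**What to change.** At all seven places in 8.2, replace the ending that sends the patient to survival follow-up (shortened to *survival follow* at the last) with: *then proceed to follow-up per Section 13 (clinical follow-up if 24 cycles are completed without PD)*.

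The cost is seven wording edits. Affected patients would attend the 3-monthly visits and tests that 13.4 already plans for completers. If survival follow-up is really intended for them, 13.0 and 13.4 must state the exception; that would remove the contradiction but leave the loss of scheduled assessments.

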#### Additional Adverse Events:

Grade  $\geq 3$  non-hematological toxicity (other than peripheral neuropathy) considered at least probably related to ixazomib:

- Omit ixazomib until resolution to Grade  $\leq$  1 or baseline, then restart at the same dose.
- If not recovered to  $\leq$  Grade 1 or baseline despite adequate supportive care within 4 weeks, then the patient may continue on single-agent ibrutinib till the completion of treatment and then proceed to survival follow-up.
- For reoccurrence of  $\geq 3$  non-hematological toxicity (other than peripheral neuropathy) omit ixazomib until resolution to Grade  $\leq$  1 or baseline, then restart at one lower dose level.
- **For  $\geq 3$  nausea, vomiting or diarrhea:** Once the ixazomib is omitted and the toxicity recovers to Grade  $\leq$  1 or baseline within 4 weeks of holding ixazomib, it should be restarted at one lower dose level.
- Once ixazomib is reduced for any toxicity, the dose may not be re-escalated. If it is ultimately determined that therapy with ixazomib is no longer safe, the patient may continue on ibrutinib until completion of treatment and then proceed to survival follow.

- If multiple AEs are seen, administer the dose based on the greatest reduction required by any single AE observed. Dose modifications are for AEs attributed to study treatment only. Dose modifications are not required for AEs if they are deemed unlikely or unrelated to study treatment.

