## 8.0 Dosage Modification Based on Adverse Events

A dose of ixazomib and ibrutinib (as per attribution by the treating physician) is held if a patient experiences any of the following considered at least possibly related to ixazomib and/or ibrutinib at the beginning of a new cycle of treatment:

- ANC <1,000/mm^3 (grade 2)
- Platelet <75,000/mm^3 (grade 1)
- Any other nonhematologic toxicity (except for alopecia or fatigue)  $\geq$  grade 3 with the

following considerations:

- Grade 3 nausea, vomiting or diarrhea will be considered significant if they occur despite appropriate maximal anti-emetic and/or antidiarrheal therapy.
- Grade 3 hyperglycemia will be considered significant if the patient is symptomatic or glucose level is >300 mg/ml despite appropriate administration of insulin and/or oral antidiabetic agents.

→ **ALERT:** **ADR reporting may be required for some adverse events (See Section 10.0)** ←

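### Section 8.2 requires ixazomib omission for grade 3+ non-haematologic toxicity only from *probable* attribution, so a mid-cycle event rated *possible* requires no omission of the day 8 or day 15 dose

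*Combined protocol and SAP*

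**What the plan says.** Section 8.2, under its list of additional adverse events, covers grade 3 or worse non-haematologic toxicity other than peripheral neuropathy that is "considered at least probably related to ixazomib". The first bullet omits ixazomib until recovery to grade 1 or baseline and then restarts it at the same dose. Later bullets reduce the dose by one level on recurrence, and also after grade 3 or worse nausea, vomiting or diarrhoea. A reduced ixazomib dose may not be raised again. The closing bullet limits dose modification to events attributed to study treatment and exempts those rated unlikely or unrelated.

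Section 8.0 holds doses for events "at least possibly related to ixazomib and/or ibrutinib at the beginning of a new cycle of treatment". Its non-haematologic trigger is also grade 3 or worse, with alopecia and fatigue excepted.

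Section 8.3 omits ibrutinib for the same grade of non-haematologic event once it is at least possibly related to ibrutinib, at any point in the cycle and with the same two exceptions. The early safety analysis (16.4) and the adverse event stopping rule (16.52) both count events from *possible* upward.

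Ixazomib is taken on days 1, 8 and 15 of each 28-day cycle (1.4 and Table 7.1a). Section 7.0 has patients take both drugs themselves.

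**The concern.** The 8.2 threshold is out of line with the protocol's other rules for the same kind of event. Only the day 1 dose falls under the cycle-start check in 8.0. For days 8 and 15 the governing text is 8.2, and it is silent on an event rated *possible*.

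That rating is foreseeable. Section 15 lists diarrhoea, nausea, vomiting, rash and peripheral oedema as common with both drugs, so a physician may well rate a shared toxicity *possible* for each. If the event meets the 8.3 conditions, ibrutinib is then omitted mid-cycle while nothing requires the same for ixazomib. In cycle 1, such an event can also count towards lowering the study's ixazomib dose under 16.4 without obliging that patient to skip the next dose.

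Patient safety is at stake. After cycle 1 the test schedule lists no visit on days 8 or 15, so the written rule is what staff would consult when a patient calls with a severe event.

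**Working it through.** **1. The rules side by side**

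| Section | Drug | Lowest attribution | When it applies | Consequence |
|---|---|---|---|---|
| 8.0 | Ixazomib and/or ibrutinib | Possible | Start of a cycle only | Dose held |
| 8.2, additional events | Ixazomib | Probable | Any time | Omit, then same dose; reduce on recurrence or after the named gastrointestinal events |
| 8.3, additional events | Ibrutinib | Possible | Any time | Omit, then same dose; reduce on recurrence |
| 16.4 | Combination | Possible | Cycle 1 | Counts towards de-escalation |
| 16.52 | Combination | Possible | Any time | Counts towards suspending accrual (grade 4 or higher) |

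The table rows in 8.2 for cytopenias, febrile neutropenia and neuropathy state no *probable* threshold.

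**2. A mid-cycle grade 3+ non-haematologic event other than neuropathy, by its rating for ixazomib**

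- Definite or probable: ixazomib is omitted under 8.2.
- Possible: no ixazomib action is required on day 8 or 15. If the event persists, 8.0 applies at the next cycle start.
- Unlikely or unrelated: no modification, by the closing bullet of 8.2.

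The middle category is the gap. No other section fills it.

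**3. Doses exposed per event**

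Inputs: ixazomib 4 mg on days 1, 8 and 15; 28-day cycles; next 8.0 check on day 29. Assumptions that the documents do not supply: onset is equally likely on each of days 1 to 28 and follows any dose taken that day, and the event lasts *L* days. A dose on day *x* (8 or 15) is exposed by onset on day *d* if *d* < *x* ≤ *d* + *L*.

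- Maximum: onset on days 1 to 7 with a long enough event exposes both doses, 2 × 4 mg = 8 mg.
- *L* = 3: onset on days 5–7 exposes day 8, and onset on days 12–14 exposes day 15. Mean (3 + 3)/28 = 0.21 doses.
- *L* = 7: onset on days 1–7 exposes day 8, and onset on days 8–14 exposes day 15. Mean (7 + 7)/28 = 0.50.
- *L* = 14 or more: onset on days 1–7 exposes day 8, and onset on days 1–14 exposes day 15. Mean (7 + 14)/28 = 0.75.
- Onset on days 15–28 exposes no dose before the next check.

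The plan states no figure of its own to reproduce. It also gives no rate for events rated *possible*, so a total across the trial cannot be calculated.

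**The case against.** The strongest counter-argument is that 8.2 already covers these events. Its closing bullet divides events into those attributed to treatment and those rated unlikely or unrelated, which would put *possible* on the side that needs modification. That reading is available. But the bullet names no action for such events, and it conflicts with the threshold stated above it. If *possible* was meant to be covered, that is a reason to correct the threshold.

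Second, a higher bar for ixazomib could be deliberate. Its reductions are permanent, whereas ibrutinib may be re-escalated under 8.3, and a first reduction from 4.0 to 3.0 mg costs (4.0 − 3.0)/4.0 = 25% of the dose. The protocol does not give this reason, but it has force for the reduction steps. It has little force for the first bullet, which skips doses and resumes at the same level. The *probable or definite* standard for bleeding in 8.3 governs discontinuation, so it is no precedent for omission.

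Third, the window is narrow, and clinicians may act without a rule. In 8.2 ixazomib can be stopped when judged no longer safe, and 13.3 allows withdrawal in the patient's interest. Cycle 1 has adverse event monitoring on days 8, 15 and 22. Nothing forbids omission for an event rated *possible*. This limits the severity. However, the discretionary provisions concern ending treatment and set no rule for skipping a single dose.

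A reader might also infer a clash between holding under 8.0 and omitting under 8.2. On omission, 8.2 says "The patient does not make up the omitted dose(s) at a later time", and on hold or delay, "The patient does make up the delayed dose(s) when the patient meets the protocol criteria to restart drugs". These definitions are introduced with "Use the following to describe actions in the Action column", and 8.0 has no such column. Carrying them over to 8.0 is an inference, and this point does not rest on it.

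**Conclusion.** The inconsistency is real and follows from the text alone. For this class of toxicity, the plan requires no omission of a day 8 or day 15 ixazomib dose when the event is rated *possible*. Severity is minor: at most 2 doses (8 mg) per event, and on average 0.21 to 0.75 doses for durations from 3 days to 14 or more, under the uniform-onset assumption. The maximum needs only the dosing calendar. Sample size, significance level and power do not depend on the gap.

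Two stronger readings are not supported. The plan does not direct that ixazomib be continued through such an event; it only fails to require omission. And although 2 × 24 = 48 of the 3 × 24 = 72 planned doses fall on days 8 and 15, that is the share of scheduled doses outside the cycle-start check. It does not measure how many doses would be taken during toxicity.

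**What to change.** In the additional adverse events part of 8.2, lower the attribution threshold from probably to possibly related to ixazomib for the first bullet only: omit until grade 1 or baseline, then restart at the same dose. For events rated *possible*, except alopecia and fatigue, as 8.0 and 8.3 already do. State that the one-level reductions, on recurrence and after grade 3 or worse nausea, vomiting or diarrhoea, still require at least *probable* attribution. Sections 8.0, 8.3, 16.4 and 16.52 need no change.

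The cost is a short wording edit and a few extra skipped ixazomib doses that are not made up, up to 2 per event before the next cycle start. The edit adds no permanent reductions for events rated *possible*. One asymmetry remains: grade 3 fatigue would lead to omission if rated *probable* but not if rated *possible*. That is the price of leaving the present rule for *probable* events untouched. If the sponsor does intend the higher bar for omission as well, 8.2 should say so, give the reason, and bring the closing bullet into line.
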